4.3.3. Sensitivity Analyses

A multiple imputation-based tipping-point sensitivity analysis is specified in Section 4.1.2.1.1 (MI-TP).

Additionally, the primary efficacy measure analyses specified in Section 4.3.2 that are conducted using the apo(a) assay data will be repeated, excluding participants at Chinese sites. This sensitivity analysis aims to evaluate the impact on the results from excluding participants at Chinese sites from the primary efficacy analyses conducted using the intact Lp(a) assay data.

4.4. Secondary Endpoints Analysis

4.4.1. **Definition of endpoint(s)**

The secondary study objectives are listed in Section 1.1.

4.4.2. Main analytical approach

The secondary study objectives will be analyzed with the efficacy estimand using the analytical approaches specified in Section 4.1.2.1. The clinical measures for secondary endpoints may be log-transformed before statistical analyses, if deemed necessary. Specifically, percent change from baseline to Week 12 for Apo(B) and hsCRP will be analyzed by MMRM model. The proportion of participants achieving Lp(a) < 125 nmol/L at Week 12 will be analyzed by logistic regression model.

For each hypothesis, LY3473329 will be declared superior to placebo if the p-value is less than 0.05.

LY3473329 concentration data will be analyzed using a population PK approach via nonlinear mixed-effects modeling with the NONMEM software. The relationships between LY3473329 dose and/or concentration and efficacy, tolerability, and safety endpoints may be characterized. Additionally, the impact of intrinsic and extrinsic participant factors, such as age, weight, gender, and renal function on PK and/or PD parameters, may be examined as needed.

4.5. Tertiary/Exploratory Endpoints Analysis

Unless otherwise specified, exploratory analyses will be conducted with the efficacy estimand using the analytical approaches specified in Section 4.1.2.1. Percent change in lipid profile and change in plasminogen activity will be analyzed by the MMRM. Analyses for proportion of participants achieving Lp(a) lowering of at least 150 nmol/L at Week 12 will be conducted using the logistic regression model. Change in SF-36v2 acute form domain scores will be analyzed by the ANCOVA model specified in Section 4.1.2.1, with last observation carried forward (LOCF) used for imputation of missing values at Week 12.

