Continuous data will be summarized using the sample size, mean, SD, median, minimum, and maximum. The analysis model to make comparisons among treatment groups relative to continuous measurements assessed over time, in addition to the baseline and end-of-treatment measurements, will be a mixed model for repeated measures (MMRM).

The model terms are

- treatment
- visit
- treatment-by-visit interaction
- baseline-by-visit interaction
- baseline measurement
- baseline Lp(a) stratum (<275 nmol/L, $\ge 275 \text{ nmol/L}$), and
- country or region.

Analysis of covariance (ANCOVA) may be used to make comparisons among treatment groups for continuous measurements with only 1 post-baseline assessment. In this case, ANCOVA will be conducted with available data and missing values will not be imputed in the analysis.

Categorical data

Categorical data will be summarized by sample size, frequency, and percentage. Fisher's exact test will be used to examine the treatment difference in categorical outcomes. Logistic regression may be used to examine the treatment difference in binary efficacy outcomes. The negative binomial regression model may be used for the treatment comparison of discrete count measures if deemed appropriate. Participant-specific random effects may be added to the logistic and the negative binomial regression models if longitudinal measurements are available. Model terms in the longitudinal logistic or negative binomial regression models are the same as in the MMRM.

Other statistical methods may be used, as appropriate, and details will be documented in the SAP.

Handling of missing, unused, and spurious data are addressed prospectively in the overall statistical methods described in the protocol and in the SAP, where appropriate. Adjustments to the planned analyses are described in the final CSR.

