9.3.4. Exploratory Endpoint(s) Analysis

Exploratory endpoints are listed in Section 3.

The continuous clinical measures, including change in lipid profile and change in plasminogen activity, will be analyzed using an MMRM. Baseline measures will be used for adjustment. The change in SF-36v2 acute form domain scores will be analyzed using an ANCOVA model. Baseline domain scores will be used for adjustment. Analyses for proportion of participants achieving Lp(a) lowering of at least 150 nmol/L at Week 12 will be conducted using a longitudinal logistic regression model described in Section 9.3.1.

Details of other analyses used for the exploratory objectives will be provided in the SAP.

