2.1. Multiplicity Adjustment

Treatment comparisons will be performed for the primary objective at the full significance level of 0.05. No multiplicity adjustments will be made for the analysis of secondary and exploratory objectives.

3. Analysis Sets

This table defines the analysis population and datasets for the purposes of analysis.

Population	Description
Screened	All participants who sign the ICF.
Randomized	All participants who are randomly assigned to a treatment arm.
Efficacy Analysis Set (EAS)	Data obtained during treatment period from all randomly assigned participants who are exposed to at least 1 dose of double-blind study treatment. Excludes data after discontinuation of study drug or initiation of Lp(a) modifying medication.
Full Analysis Set (FAS)	Data obtained during the treatment period from all randomly assigned participants who are exposed to at least 1 dose of intervention, regardless of adherence to intervention or initiation of Lp(a) modifying medication.
Safety Analysis Set (SS)	Data obtained during the treatment period plus safety follow-up from all randomly assigned participants who are exposed to at least 1 dose of intervention, regardless of adherence to intervention or initiation of Lp(a) modifying medication.

Abbreviation: ICF = informed consent form.

4. Statistical Analyses

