For categorical measures, summary statistics will include sample size, frequency, and percentages. A logistic regression model will be used to examine the treatment difference in binary efficacy outcomes with missing endpoints imputed. Fisher's exact test or Pearson's chi-square test will be used for treatment comparisons in other categorical outcomes.

Data may exist at visits where the variable was not scheduled to be collected. In these situations, data from the early discontinuation visit that does not correspond to the planned collection schedule will be excluded from the mixed model repeated measures (MMRM), analysis of covariance (ANCOVA), or logistic regression analysis, unless otherwise specified.

Endpoints that compare treatment groups based on percent change from baseline will be conducted by log-transformation of the dependent variables. Standard errors and 95% CIs will be constructed using the delta method. The LS means and standard error for each treatment,

Page 11

difference in LS means between arms, and corresponding 95% CIs will be calculated as shown in Table EKBC.4.1, where $\bar{Z}_{b.}$ is the arithmetic mean of the baseline of the log of the response, $\hat{\mu}_{\Delta Z,k}$ and $\widehat{SE}_{\Delta Z,k}$ are the estimates and standard errors of change from baseline on the log scale for treatment group k, and $\hat{\mu}_{\Delta Z,k vs R}$, $\widehat{SE}_{\Delta Z,k vs R}$, $L_{\Delta Z,k vs R}$, and $U_{\Delta Z,k vs R}$ are the estimates, standard errors, lower and upper confidence limits for the comparison of treatment group k versus placebo.

Quantity		Change from Baseline	Percent Change from Baseline
Within	Estimate	$\left[\exp\left(\hat{\mu}_{\Delta \mathbf{Z},k}\right) - 1\right]\exp(\bar{Z}_{b})$	$\left[\exp(\hat{\mu}_{\Delta \mathrm{Z},k})-1 ight] imes 100$
l reatment	SE	$\exp(\overline{Z}_{b})\exp(\hat{\mu}_{\Delta Z,k})\cdot\widehat{SE}_{\Delta Z,k}$	$\exp(\hat{\mu}_{\Delta Z,k}) \cdot \widehat{SE}_{\Delta Z,k} imes 100$
	P-value	NR	p_k
Between- Treatment	Estimate	$[\exp(\hat{\mu}_{\Delta Z,k}) - \exp(\hat{\mu}_{\Delta Z,R})] \cdot \exp(\bar{Z}_{b.})$	$(\exp(\hat{\mu}_{\Delta Z,k \ vs \ R}) - 1) \times 100$
(Treatment k vs. Reference Arm)	SE	$e^{\bar{Z}_{b}}\sqrt{e^{2\hat{\mu}_{\Delta Z,k}}\cdot\left(\widehat{SE}_{\Delta Z,k}\right)^{2}+e^{2\hat{\mu}_{\Delta Z,R}}\cdot\left(\widehat{SE}_{\Delta Z,R}\right)}$	$\exp(\hat{\mu}_{\Delta Z,k \ vs \ R}) \cdot \widehat{SE}_{\Delta Z,k \ vs \ R} \times 100$

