4.1.2. Analysis methods

4.1.2.1. Analysis method for efficacy estimand

Unless otherwise specified, the primary endpoint, secondary endpoints, and exploratory endpoints will be analyzed according to the efficacy estimand, which represents the efficacy had participants adhered to the randomized treatment without initiating Lp(a) modifying medications. Considered Lp(a) modifying medications are listed in Table EKBC.4.3. The assessment of efficacy measurements guided by the efficacy estimand will be conducted using the EAS (Section 3).

Table EKBC.4.3. Lp(a) Modifying Medica	tions
--	-------

Category	Medication
Lp(a)-Altering therapies	 statins PCSK9 inhibitors prescription-dose niacin mipomersen testosterone, estrogens, anti-estrogens, progestins, selective estrogen receptor modulators, or growth hormone
Excluded Treatment Medical Devices, and/or Procedures	 lipid apheresis any investigational drug, biological agent, or device other than study provided investigational product

A restricted maximum likelihood-based, mixed-effect model repeated measures (MMRM) analysis will be used to analyze continuous longitudinal endpoints. All the longitudinal observations at each scheduled postbaseline visit will be included in the analysis. The MMRM model will include the fixed class effects of treatment group (LY 10 mg, LY 60 mg, LY 240 mg, and placebo), strata (country and baseline Lp(a) stratum [<275 nmol/L, \geq 275 nmol/L as measured by the apo(a) assay]), visit, and treatment-by-visit interaction, as well as the continuous baseline value. An unstructured covariance structure will be used to model the within-participant errors. Significance tests will be based on LS means and Type III tests. If this analysis fails to converge, the following covariance structures will be tested in order:

- 1. Toeplitz with heterogeneity
- 2. autoregressive with heterogeneity
- 3. compound symmetry with heterogeneous variances
- 4. Toeplitz
- 5. autoregressive, and
- 6. compound symmetry without heterogeneous variances.

The first covariance structure that converges will be used. The Kenward-Roger approximation will be used to estimate denominator degrees of freedom.

If the data does not warrant the MMRM model, then an ANCOVA model with treatment group, strata, and the continuous baseline value will be used to analyze the continuous endpoint. Data for participants with missing values at Week 12 will be imputed using the multiple imputation

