method under the MAR assumption. Estimates and standard errors from multiple imputed datasets will be combined using Rubin's rules.

For binary endpoints derived from a continuous variable, the missing value in the underlying continuous variable will be imputed first based on the missing at random assumption (MAR), and then the corresponding binary variable will be derived.

A logistic regression model with treatment group and strata as fixed effects and the continuous baseline value as a covariate will be used to examine the treatment difference with missing endpoints imputed. The unconditional treatment group effect will be assessed by risk difference and relative risk using the marginal standardization method, where the treatment group-specific risk will be derived from the counterfactual risks for each participant that are predicted with the fitted logistic model (Ye et al. 2023). The estimated treatment group-specific risk, risk difference, relative risk, p-value and 95% CI will be presented.

For endpoints involving Lp(a), the Lp(a) strata class effects will be excluded from the above models.

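### LOCF for missing Week 12 SF-36 scores is an undeclared departure from the protocol's available-data ANCOVA and does not estimate the efficacy estimand

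*SAP*

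**What the plan says.** **Protocol.** Section 9.3.4 states: "The change in SF-36v2 acute form domain scores will be analyzed using an ANCOVA model". Section 9.3.1, on measures with a single post-baseline assessment, states: "ANCOVA will be conducted with available data and missing values will not be imputed in the analysis". The Schedule of Activities places SF-36 at Visit 2 (baseline), Visit 7 (Week 12) and the ED visit, with nothing at Visits 3 to 6.

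**SAP.** Section 4.5 opens with a default: "Unless otherwise specified, exploratory analyses will be conducted with the efficacy estimand using the analytical approaches specified in Section 4.1.2.1". For SF-36 it then names the ANCOVA of Section 4.1.2.1, "with last observation carried forward (LOCF) used for imputation of missing values at Week 12". The rule attached to that ANCOVA in Section 4.1.2.1 is different: "Data for participants with missing values at Week 12 will be imputed using the multiple imputation". That rule takes the data to be missing at random and pools the results by Rubin's rules.

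Two further rules decide which score could be carried forward. The Efficacy Analysis Set (EAS) in SAP Section 3: "Excludes data after discontinuation of study drug or initiation of Lp(a) modifying medication". SAP 4.1, on MMRM, ANCOVA and logistic regression: "data from the early discontinuation visit that does not correspond to the planned collection schedule will be excluded", with an allowance for other specification.

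SAP 1.1 gives exploratory objectives an efficacy estimand like the primary one. Discontinuing the intervention and starting an Lp(a)-modifying drug are both handled by the hypothetical strategy. SAP Sections 1 and 4.9 each declare no change from the protocol's analyses. No reason for LOCF is given.

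**The concern.** The protocol and the SAP give different missing-data rules for the same ANCOVA, while the SAP says that nothing has changed. An analyst cannot follow both.

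The choice also affects what is estimated. The hypothetical strategy asks what the Week 12 score would have been had the participant stayed on treatment without new Lp(a)-modifying medication. A score from before treatment, or from around the time of stopping, does not answer that. With no SF-36 between baseline and Week 12, the carried score is often the baseline score. The participant then enters the analysis as an observed change of exactly zero. At stake are the size of the estimated SF-36 effect and the width of its interval.

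**Working it through.** **1. The plan's own figures.** 233 randomized 1:2:2:2 with 10% dropout: 233/7 × 0.9 = 29.96 completers on 10 mg, and 466/7 × 0.9 = 59.91 in each other arm. This reproduces the stated 30 and 60. The documents give no SD, effect or correlation for SF-36.

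**2. Which score is carried.** Under any reading it is baseline for three groups:
- participants still on drug who miss the Visit 7 form;
- participants lost without an ED visit;
- participants who start an Lp(a)-modifying drug but stay on study drug to Visit 7. The EAS removes their observed Week 12 score and LOCF puts baseline in its place.

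For participants who do attend an ED visit, it is baseline if the EAS rule and the ED-visit rule of SAP 4.1 exclude the ED score. The SAP does not settle this.

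**3. Expected difference if baseline is carried.** Let d be the proportion missing (completely at random) and Δ the true mean change, with t for treated and p for placebo:

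E(difference) = (1 − d_t)Δ_t − (1 − d_p)Δ_p

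- Equal dropout of 5%, 10% or 20% multiplies the effect by 0.95, 0.90 or 0.80.
- Both arms change by +3, dropout 20% v 5%: 0.80 × 3 − 0.95 × 3 = −0.45, where the truth is 0.
- Changes +3 v +2, dropout 5% v 20%: 0.95 × 3 − 0.80 × 2 = 1.25, where the truth is 1.00.

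**4. Simulation.** ANCOVA of change on treatment and baseline, 4,000 runs per case, values missing completely at random. Assumed: SD 10, baseline-to-Week-12 correlation 0.5, 0.7 or 0.85, true effect 3 points. Case shown: 67 v 67 with 10% dropout in each arm.

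| Correlation | Method | Mean estimate | 95% CI width | Power | Coverage |
|---|---|---|---|---|---|
| 0.5 | Available data | 2.985 | 6.252 | 0.461 | 0.948 |
| 0.5 | Baseline carried | 2.690 | 5.720 | 0.451 | 0.944 |
| 0.7 | Available data | 3.022 | 5.166 | 0.629 | 0.948 |
| 0.7 | Baseline carried | 2.716 | 4.698 | 0.625 | 0.943 |
| 0.85 | Available data | 3.007 | 3.807 | 0.872 | 0.949 |
| 0.85 | Baseline carried | 2.708 | 3.460 | 0.865 | 0.936 |

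Width ratios, baseline carried to available data: 5.720/6.252 = 0.915, 4.698/5.166 = 0.909, 3.460/3.807 = 0.909, so about 9% narrower. With no missing data at all the widths were 5.918, 4.890 and 3.603, so the carried-baseline intervals are 3% to 4% narrower than complete follow-up would give.

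With a true effect of 0 and equal 10% dropout, type I error was 0.049, 0.052 and 0.049. The 33 v 67 comparison for 10 mg shows the same pattern (estimates 2.717 to 2.738, coverage 0.940 to 0.946). At 20% dropout in each arm, 67 v 67, estimates were 2.378 to 2.427 and coverage 0.888 to 0.932.

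**5. Why coverage falls.** With baseline carried, the model SE agrees with the actual spread of the estimates (1.446 v 1.456, 1.187 v 1.189, 0.875 v 0.883). The SE is right for the attenuated quantity. Coverage falls because the interval is centred on about 2.7, not 3.

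**6. Unequal dropout.** Both arms +3, 20% v 5%: mean estimates −0.450, −0.437 and −0.439, with type I error 0.059, 0.074 and 0.081. Available data gave 0.045, 0.055 and 0.054. The Monte Carlo SE at 5% is √(0.05 × 0.95/4000) = 0.003.

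**7. If ED scores are carried.** Suppose an ED score shows a fraction f of the Week 12 effect. With equal dropout the multiplier is 1 − d(1 − f). For d = 10% and an illustrative f = 0.5 this is 0.95, against 0.90 when baseline is carried.

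**The case against.** A reader might infer that LOCF in this schedule is always baseline carried forward. The documents do not establish that. SF-36 is scheduled at the ED visit. The exclusion in SAP 4.1 is introduced for visits at which a variable was not due, and it yields to other specification, which an explicit LOCF clause could be. The EAS rule points toward exclusion, but the SAP does not say whether a form completed at the ED visit falls after discontinuation. This objection stands: step 4 holds only if baseline is carried.

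A reader might also infer that the SAP contradicts itself. It does not. SAP 4.5 applies the Section 4.1.2.1 methods unless otherwise specified, and then specifies LOCF. That is an unexplained exception to multiple imputation under MAR. The conflict is with the protocol. Protocol 9.3.1 does let the SAP change non-principal methods, but it expects the change to be described and justified, and the SAP declares none.

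A third tempting reading is that LOCF shrinks the effect. That holds for equal dropout; step 3 shows an effect enlarged from 1.00 to 1.25 under unequal dropout.

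The practical weight is modest. SF-36 is exploratory, the protocol expects discontinuation to be uncommon, and at the planned dropout the test hardly changes. Protocol 2.3.2 also warns that short-term Lp(a) lowering may bring no benefit; if SF-36 barely changes in any arm, the bias is close to zero. None of this supplies a reason to prefer LOCF.

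**Conclusion.** Wrong as written; low priority. Two faults need no simulation: LOCF conflicts with protocol 9.3.1 while SAP Sections 1 and 4.9 declare no change, and a carried score, whether baseline or ED, does not estimate the hypothetical efficacy estimand.

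The size is conditional. If baseline is carried and 10% drop out of each arm, the effect is multiplied by about 0.90, intervals are about 9% narrower than with available data, and coverage is 93.6% to 94.4%. Power and type I error are almost unchanged because estimate and SE shrink together. With 20% v 5% dropout and a common change of +3, a true zero becomes about −0.45, with type I error 5.9% to 8.1%. If ED scores are carried and show part of the effect, the bias is smaller. The SD, correlations, effect, common change and unequal dropout rates are assumptions, and missingness was taken as completely at random. The primary analysis and the sample size are unaffected.

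**What to change.** Delete the LOCF clause from SAP 4.5 and use the available-data ANCOVA of protocol 9.3.1. This restores agreement with the protocol, and SAP 4.9 needs no entry on this point.

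Alternatively, use the multiple imputation under MAR of SAP 4.1.2.1. That also departs from the protocol's no-imputation rule, so list it in SAP 4.9 with a reason and correct the no-change statement in Section 1. Multiple imputation was not simulated here.

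In either case, state in SAP 4.5 that SF-36 scores from the ED visit are not used as Week 12 values.

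The cost is one or two SAP sentences, plus the Section 1 and 4.9 edits for the second option. Under available data the intervals are about 9% wider (6.252/5.720 = 1.09), with no loss of power in the cases run (0.461 v 0.451, 0.629 v 0.625, 0.872 v 0.865).

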4.5.1. Bayesian Analyses for Dose-Response

A Bayesian dose-response analysis will be performed on the percent change from baseline at Week 12 for Lp(a).

The two-component prediction (ITP) model proposed in Fu et al. (2010) and Qu et al. (2019) will be used to estimate Bayesian dose response. The model is as follows:

$$Y_{dit} = f(t; d)(\lambda(d) + s_i) + \epsilon_{it},$$

where Y_{dit} represents the observation for subject *i* at time *t* when taking dose *d*, $\lambda(d)$ is the mean dose response function for dose *d*, s_i is the between-subject random error term, and ϵ_{it} is the within-subject random error term. The mean response function f(t; d) is modeled as

$$f(t;d) = \frac{1-e^{-k(d)t}}{1-e^{-k(d)t}max},$$

where t_{max} is the maximum duration of treatment period and k(d) is the shape parameter for dose d. $s_i \sim N(0, \sigma_s^2)$ and $\epsilon_{it} \sim N(0, \sigma^2)$ are independent, denoting between-subject variation and within-subject variation respectively. Given s_i , $Y_{dit} \sim N(f(t; d)(\lambda(d) + s_i), \sigma^2)$.

A three-parameter logistic regression model may be assumed for the dose response function, $\lambda(d)$. Let α_0 , α_1 , and α_2 represent the basal effect when the dose level is zero (placebo), the maximum effect that can be achieved by any dose level on top of placebo, and the dose level that produces half of the maximum improvement, respectively. Then, the mean function of the parameter of interest is modeled by:

$$\lambda(d) = \alpha_0 + \frac{\alpha_1 d}{\alpha_2 + d}.$$

The estimation of the parameters will be carried out in a Bayesian framework assuming noninformative priors for the hyperparameters in the model as follows:

$$\begin{cases} k(d) \sim \text{Uniform}(0,1), \\ \alpha_0, \alpha_1, \alpha_2 \sim N(0, 100^2), \\ \frac{1}{\sigma^2}, \frac{1}{\sigma_s^2} \sim Gamma(0.01, 0.01). \end{cases}$$

Posterior inference will be drawn for the dose-response of clinical interest, and the 95% credible intervals will also be plotted.

Other dose-response models for $\lambda(d)$ may be explored if the aforementioned dose-response model does not fit the data well, for example, Simple Normal Dynamic Linear Modeling (NDLM) described below.

$$\begin{cases} \lambda(d_1) \sim N(0, \tau) \\ \lambda(d_{i+1}) \sim N(\lambda(d_1), \tau), i = 1, 2 \dots \end{cases}$$

where 1,2,... are the indexes of each *i*th dose level. The first dose level prior takes on a normal distribution with a mean of 0 and a precision of τ . τ is drawn from either a normal or gamma distribution. Subsequent dose levels take on a normal distribution with the mean of the previous dose level and precision τ .

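### SAP 4.5.1 gives the half-maximum dose a prior with half its mass below zero, so ED50 and the curve below 10 mg are unreliable if 10 mg is near the plateau

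*SAP*

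**What the plan says.** SAP Section 4.5.1 commits to the analysis: "A Bayesian dose-response analysis will be performed on the percent change from baseline at Week 12 for Lp(a"). For the dose part, "A three-parameter logistic regression model may be assumed for the dose response function". It is λ(d) = α₀ + α₁d/(α₂ + d), where α₀ is the placebo response, α₁ the largest effect on top of placebo, and α₂ "the dose level that produces half of the maximum improvement".

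The priors are introduced as "assuming noninformative priors for the hyperparameters in the model as follows". The shape parameter k(d) is Uniform(0, 1), both precisions are Gamma(0.01, 0.01), and α₀, α₁ and α₂ all share N(0, 100²). Neither document truncates α₂, puts it on a log scale or otherwise requires it to be positive.

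Other dose-response forms "may be explored if the aforementioned dose-response model does not fit the data well". The example given is a normal dynamic linear model (NDLM) whose first dose level "takes on a normal distribution with a mean of 0 and a precision of" τ, where τ "is drawn from either a normal or gamma distribution".

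SAP Section 4.8 names this model among the analyses an interim may include for internal planning. Protocol Section 4.3 says the dose range is meant to support dose selection for further development.

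**The concern.** α₂ is a dose, so a negative value has no meaning under the SAP's own definition. If α₂ < 0, λ(d) has a pole at d = |α₂|, the curve changes sign across it, and α₁ is no longer the maximum effect. The rest of the prior block respects the range of its constrained parameters, so this looks like an oversight.

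What is at stake is ED50 and any curve or credible band drawn below 10 mg. The SAP's safeguard is to try other models when the fit is poor. It would not reliably catch this, because a small negative α₂ fits a plateau well.

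Two smaller points sit in the same section:

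- The NDLM text calls τ a precision but allows it a normal prior, which permits negative values. This does not cause the ED50 problem.
- Section 4.5.1 does not say whether raw or log-transformed percent change is modelled, whereas SAP Section 4.1 log-transforms percent-change comparisons.

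**Working it through.** **Inputs from the documents.** Doses 0, 10, 60 and 240 mg; 233 randomised 1:2:2:2 (10 mg the smallest arm); 10% dropout; SD 20%; a 60% difference for power (SAP Section 5). **Assumed:** the shape of the Week 12 means, which the documents do not give.

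**The plan's own figures reproduce.** 233/7 = 33.3 and 2 × 33.3 = 66.6 randomised; × 0.9 = 30.0 and 59.9 completers. The standard error of the difference is 20√(1/30 + 1/60) = 4.47 for 10 mg and 20√(2/60) = 3.65 for the other doses. The effect of 60 is 13.4 and 16.4 standard errors, so power is above 99%. Section 4.5.1 gives no operating characteristics of its own.

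**Prior (exact).** P(α₂ < 0) = Φ(0) = 0.50. P(-240 < α₂ < 0) = Φ(0) - Φ(-2.4) = 0.492, so 49% of the prior puts the pole inside the studied range.

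**Why a plateau does not remove it.** Take α₀ = 0, α₁ = -60, α₂ = -0.5. Then λ(10) = -60 × 10/9.5 = -63.2, λ(60) = -60.5 and λ(240) = -60.1. If every active arm had a true mean of -60, the 10 mg misfit is 3.2 against a standard error of 20/√30 = 3.65, or 0.9 standard errors. Yet λ(2) = -60 × 2/1.5 = -80, and λ(0.25) = -60 × 0.25/(-0.25) = +60.

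**Posterior.** α₂ on a grid, α₀ and α₁ integrated out analytically under N(0, 100²), normal likelihood on noise-free Week 12 arm means, placebo 0, known SD, 60/30/60/60 completers:

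| Means at 10/60/240 mg | P(α₂<0), SD 20 | P(α₂<0), SD 15 to 30 |
|---|---|---|
| -60/-60/-60 | 0.45 | 0.46 to 0.42 |
| -55/-60/-60 | 0.09 | 0.04 to 0.15 |
| -50/-58/-60 | 0.008 | 0.001 to 0.04 |
| -40/-58/-62 | about 0 | not run |

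Posterior mass below -10 is about 0 in every row, so every surviving pole lies between 0 and 10 mg.

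**Consequence in the flat case (SD 20; posterior means or 95% intervals).**

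| Quantity | SAP prior | Same prior, α₂ > 0 |
|---|---|---|
| ED50 (mg) | -1.25 to 1.82 | 0.03 to 2.07 |
| Effect at 2 mg | -151 to -33 | -60 to -31 |
| Effect at 5 mg | -77 to -46 | -61 to -44 |
| 10 mg mean (SD) | -59.5 (3.6) | -57.2 (2.6) |
| 60 mg mean | -60.0 | -60.4 |
| 240 mg mean | -60.1 | -60.9 |
| Maximum effect α₁ | -66.5 to -53.5 | -67.1 to -54.7 |

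A lower limit of -151% is impossible, since Lp(a) cannot fall by more than 100%. For -50/-58/-60, truncation changes little: ED50 is 0.37 to 4.88 mg against 0.47 to 4.88 mg.

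**Simulated trials.** With maximum effect -60, SD 20 and 150 trials per setting, mean P(α₂ < 0) is 0.29, 0.18, 0.04 and 0.001 for a true ED50 of 0.5, 1, 2 and 5 mg (10 mg then gives 95%, 91%, 83% and 67% of the effect). At 0.5 mg, 81% of trials leave more than 5% of the posterior below zero. With half the completers, as an interim might have, the first three become 0.31, 0.21 and 0.11.

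**Two checks on the simplifications.**

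- *Log scale* (assumed log-SD 0.2 to 0.5): P(α₂ < 0) is 0.46 to 0.41, 0.002 to 0.08 and 0 to 0.01 for the first three shapes. At log-SD 0.35 the flat-case 2 mg band is -94% to -37%, against -60% to -35% truncated.
- *Repeated visits* (weeks 1, 2, 4, 8, 12; k assumed 0.1 to 1.0 per week and known; 30% to 80% of variance between subjects): the effective SD falls to 13.7 to 19.0. P(α₂ < 0) is then 0.46 to 0.45, 0.03 to 0.08 and 0.0003 to 0.006.

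**The case against.** The analysis is exploratory, the function is optional, and Section 4.5.1 promises neither an ED50 nor an estimate below 10 mg. At interim the model is one example for internal planning, with no stopping for efficacy. The flat shape is the extreme case; the 60% in SAP Section 5 is a powering difference, not a predicted curve. At -50/-58/-60 only 0.008 of the posterior is below zero. A negative ED50 would be noticed on review. Much of the imprecision comes from having no dose between 0 and 10 mg, and truncation leaves it there.

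Most of this stands, and it limits the point to a minor one. It does not rescue the prior, which contradicts the parameter's definition and is called noninformative. The documents do not say which shape to expect, so the harmful case cannot be set aside. Noticing a negative ED50 after the fact would mean choosing a new prior with the results in view.

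The objection is also right about the cost of a log-normal alternative (median 5 mg, log-SD 2). It moves the 10 mg mean from -49.3 to -50.6 for -50/-58/-60 and from -39.4 to -40.4 for -40/-58/-62, where the SAP prior does essentially no harm.

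**Conclusion.** The concern holds, with narrow scope. That the prior puts half its mass on impossible values is certain from the SAP text. The consequence is conditional: it is large when 10 mg is at the plateau, shrinks quickly below that, and is negligible when 10 mg gives about two thirds of the full effect or less. It reaches ED50 and the curve below 10 mg only. The primary MMRM, power, the superiority rule, the maximum effect and the 60 and 240 mg estimates are essentially untouched. The bands are illustrations resting on assumed mean shapes, a known SD and Week 12 means instead of the full longitudinal model; the sign problem persists under the log-scale and repeated-visit checks. The τ prior is a separate, smaller error, and the raw-or-log question only needs clarifying.

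**What to change.** - Give α₂ a positive-support prior that reaches well below 10 mg. The simplest is N(0, 100²) truncated to α₂ > 0.
- Delete the normal option for τ and keep the gamma.
- State whether the model is fitted to raw or log-transformed percent change.
- Run one sensitivity analysis with a second positive prior, for example log-normal with median 5 mg and log-SD 2. Flag ED50 as prior-dependent if it changes by more than a factor fixed in advance. In the four shapes above, the median ED50 under these two positive priors differs 1.38-, 1.39-, 1.25- and 1.10-fold. These ratios compare the two proposed priors with each other, not either with the SAP prior.
- Show the MMRM arm means beside the model estimates, and say that no dose was studied between 0 and 10 mg.

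The work is a few lines of SAP text and code plus one extra run. The statistical cost is that a positive α₂ forces a monotone curve. In the flat case this pulls the 10 mg mean from -59.5 to -57.2 (truncated normal) or -57.8 (log-normal); on the log scale at log-SD 0.35, truncation moves it from -59.6% to -58.0%. For -50/-58/-60, truncation moves it by less than 0.1, but the log-normal moves it by about 1 point, so the log-normal is better kept as the sensitivity prior. Displaying the MMRM means makes any such shift visible.
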